7.2.5.1. Basic Information

The following information will be recorded on the case report form for each study subject:

1. State (age and sex) of the study subject
2. History of hemophilia A
 - 1) Duration of disease
 - 2) Previous exposure to plasma-derived factor VIII
 - 3) Personal history of allergic reactions to factor VIII products (within 12 months)
 - 4) Family history of hemophilia A
 - 5) Family history of factor VIII inhibitors
 - 6) Family history of allergic reactions to factor VIII products (within 12 months)
 - 7) Severity
3. Medical History
 - 1) Past history and present illness
4. Concomitant Drug/Therapy
 - 1) Drug administered concomitantly with Xyntha Solofuse prefilled syringe
 - 2) Therapy given concomitantly with Xyntha Solofuse prefilled syringe infusion

5. Administration conditions of Xyntha Solofuse prefilled syringe
 - 1) Prophylactic Therapy
 - 2) Administration conditions of Xyntha Solofuse prefilled syringe (on-demand treatment: surgery and bleeding)
6. Laboratory tests: Blood test, biochemistry test (including inhibitors), urinalysis
7. Study site code: Enter the assigned code number.
8. Department code name: Enter the assigned code number.
9. Study subject ID: The investigator will sequentially assign each subject a subject identification number, a 4-digit number. Pfizer will allocate the total number of cases that need to be collected to each study site at the time of signing the contract with each site.
10. Signature of the investigator: The contracted investigator must sign the case report form after reviewing it.

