7.2.4. Administration and Dosage

This drug should be initiated under the supervision of a physician experienced in the treatment of hemophilia A.

This drug is appropriate for use in adults and children of all ages, including newborns.

Formula

$$\begin{array}{rclclclcl} \text{Required} & = & \text{body} & \times & \text{desired factor VIII rise} & \times & 0.5 \\ \text{units} & & \text{weight} & & \text{(IU/dL or normal \%)} & & \text{(IU/kg per IU/dL)} \\ & & \text{(kg)} & & & & \end{array}$$

Precise monitoring of the replacement therapy by means of plasma factor VIII activity assay should be considered, particularly for surgical intervention.

Dosing for Bleeding and Surgery

In the cases of the following hemorrhagic events, consideration should be given to maintaining the factor VIII activity at or above the plasma levels (in % of normal or in IU/dL) for the indicated period, as outline in the following table.

<Maintenance of Factor VIII Activity for Various Hemorrhagic Events>

Degree of Hemorrhage/ Type of surgical procedure	Factor VIII Level Required (% or IU/dl)	Frequency of Doses (hours) /Duration of Therapy (days)
Bleeding Early hemathrosis, minor muscle or oral bleeds	20-40	Repeat every 12 to 24 hours as necessary until resolved. At least 1 day, depending upon the severity of the bleeding episode.
Bleeding into muscles. Bleeding into the oral cavity. Mild head trauma.	30-60	Repeat infusion every 12 to 24 hours for 3-4 days or until adequate local hemostasis is achieved.
Gastrointestinal bleeding. Intracranial, intra-abdominal or intrathoracic bleeding. Fractures.	60-100	Repeat infusion every 8 to 24 hours until bleeding is resolved.
Surgery Minor operation (including tooth extraction)	30-60	Repeat infusion every 12 to 24 hours for 3-4 days or until adequate local hemostasis is achieved. For tooth extraction, a single infusion plus oral antifibrionlytic therapy within 1 hour may be sufficient.
Major operation	60-100	Repeat infusion every 8 to 24 hours until threat is resolved, or in the case of surgery, until adequate local hemostasis and wound healing are achieved. Then continue therapy for at least another 7 days to maintain the factor VIII activity at 30 to 60% (IU/dl)

Dosage for Prophylaxis

This drug has been administrated prophylactically in a pivotal clinical trial in adolescent and adult previously treated patients at a dose of 30 ± 5 IU/kg given 3 times weekly.

Administration

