This drug is administered by intravenous (IV) infusion after reconstitution of the freeze-dried powder with the diluent (0.9% Sodium Chloride). Both the Xyntha powder and the diluent are supplied within the prefilled dual-chamber syringe.

Patients administered Xyntha Solofuse prefilled syringe 250 IU, 500 IU, 1000 IU, 2000 IU, or 3000 IU at least once in the routine practice will be observed. All the enrolled subjects

should meet the general prescription criteria of Xyntha Solofuse prefilled syringe according to the local product document, and should be included in this study based on the judgment of the investigator.

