4.1. Demographics and Baseline Characteristics

- 1) State (age and sex) of the study subjects

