6.7. Efficacy Analyses

A descriptive summary will be performed for efficacy endpoint.

- 1) On-demand treatment (surgery)
 - ① The best responses to all the injection of the Xyntha Solofuse prefilled syringe used to treat bleeding (4 point scale: excellent, good, moderate, and no response) will be presented in frequency and percentage.
 - ② Number of observations of less than expected therapeutic effect (LETE) will be presented by n, mean, SD, median, minimum and maximum or frequency and percentage.
 - ③ Mean infusion dosage will be presented by n, mean, SD, median, minimum and maximum.
- 2) On-demand treatment (bleeding)
 - ① The best responses to all the injection of the Xyntha Solofuse prefilled syringe used to treat bleeding (4 point scale: excellent, good, moderate, and no response) will be presented in frequency and percentage.
 - ② Number of observations of less than expected therapeutic effect (LETE) will be presented by n, mean, SD, median, minimum and maximum or frequency and percentage.
 - ③ The number of infusions of Xyntha Solofuse prefilled syringes used to treat each new bleeding episode is descriptive statistics of medication treatment duration will be presented in n, mean, SD, median, minimum and maximum or frequency and

Statistical Analysis Plan for rPMS

percentage.

- ④ Mean infusion dosage will be presented by n, mean, SD, median, minimum and maximum.

3) Prophylactic Therapy

- ① Subjects who have experienced bleeding (overall, spontaneous) will be presented in frequency and percentage.

- ② Annualized Bleeding Rates (ABRs)

The annualized bleeding rate is the incidence rate of bleeding per year. Since the follow up period for each patient is 6 months (= 0.5 year), the ABR is calculated as follows.

N=Number of patients who received prophylactic treatment.

X=Number of patients who have bleeding among the patients included in the patients who received prophylactic treatment

$$ABRs = \frac{X}{N \times 0.5}$$

- ③ Number of observations of less than expected therapeutic effect (LETE) will be presented by n, mean, SD, median, minimum and maximum or frequency and percent.
- ④ Mean infusion dosage will be presented by descriptive statistics as n, mean, SD, median, minimum and maximum.
- ⑤ Total factor consumption (total infusion dosage) will be presented by descriptive statistics as n, mean, SD, median, minimum and maximum.

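### Infusion dose and total factor consumption are summarised with no stated unit and no scaling for body weight or observed time, and body weight is not a listed data item

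*Protocol*

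**What the plan says.** Protocol 7.2.4 gives a dose formula that multiplies body weight by the desired factor VIII rise and by 0.5. It describes prophylaxis in a pivotal trial "at a dose of 30 ± 5 IU/kg given 3 times weekly". It also states: "This drug is appropriate for use in adults and children of all ages, including newborns". The inclusion criteria in Protocol 7.2.1 set no age limit, and the syringes observed are "250 IU, 500 IU, 1000 IU, 2000 IU, or 3000 IU".

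Protocol 7.3.3 names mean infusion dosage (on-demand and prophylaxis) and total factor consumption (prophylaxis) as efficacy variables, and SAP 4.7 repeats them. For the analysis, SAP 6.7 says "Mean infusion dosage will be presented by n, mean, SD, median, minimum and maximum" and "Total factor consumption (total infusion dosage) will be presented by descriptive statistics as n, mean, SD, median, minimum and maximum". SAP 6.5 treats single and total infusion dosage in the same way, split only by on-demand or prophylactic use, with duration of administration summarised beside them. None of these places gives a unit, a per-kilogram version or a per-time version.

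The subject characteristics listed for collection are "State (age and sex) of the study subject" in Protocol 7.2.5.1 and "State (age and sex) of the study subjects" in SAP 4.1. Body weight is in neither list, nor in the demographic tables of SAP 6.1.

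Under Protocol 7.1, data run for up to 6 months from the first dose. If treatment stops earlier, records count only up to 30 days after the last dose.

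**The concern.** When dose is set by weight, a dose total that is not divided by weight reflects both how the product is used and how large the patients are. When subjects are observed for different lengths of time, an undivided total also reflects how long each was followed. Two named efficacy variables would then be reported in a form that cannot be compared between subjects of different size. They also could not be compared with the per-kilogram prophylaxis figure in the protocol, the only one it offers as a benchmark. A reader of the final report could not tell whether a low mean dose meant sparing use or small patients, or whether a low total meant low use or early stopping.

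**Working it through.** **1. Figure to reproduce.** There is none. Protocol 7.5 says that no sample size calculation applies, and neither document states an expected dose, weight or age distribution.

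**2. Effect of weight.** The 30 IU/kg, 3 times weekly, comes from Protocol 7.2.4 and is used only as a scale. The weights are assumed. Six months is taken as 26 weeks, so infusions = 3 × 26 = 78.

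| Assumed weight | IU per infusion | IU over 26 weeks | IU/kg over 26 weeks |
|---|---|---|---|
| 10 kg | 30 × 10 = 300 | 300 × 78 = 23,400 | 2,340 |
| 70 kg | 30 × 70 = 2,100 | 2,100 × 78 = 163,800 | 2,340 |

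Use is identical per kilogram, yet the unscaled figures differ 7-fold.

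**3. Effect of time.** Take two 70 kg patients on that regimen, one treated for 26 weeks and one (assumed) for 13. Their totals are 163,800 IU and 2,100 × 3 × 13 = 81,900 IU. Per treated week both are 6,300 IU. If the denominator also includes the 30 days after the last dose, the second becomes 81,900 / (13 + 30/7) = 4,738 IU per week. The denominator therefore has to be defined as well as introduced.

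**4. How much of the spread weight could explain.** A simulation of 400,000 draws took IU = weight × IU/kg. Its assumptions, none of them in the documents, were: child weight uniform from 3.5 to 60 kg; adult weight normal with mean 68 and SD 11 kg; prophylaxis dose with mean 30 and SD 5 IU/kg (reading the ± 5 as an SD); on-demand dose uniform from 10 to 50 IU/kg (required levels of 20 to 100 IU/dL, treated as the rise, × 0.5). The table gives the share of variance in unscaled IU explained.

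| Share of children | Prophylaxis: weight | Prophylaxis: child/adult status | On-demand: weight |
|---|---|---|---|
| 0% | 48% | 0% | about 15% |
| 10% | 67% | 32% | 28% |
| 30% | 81% | 51% | about 45% |
| 50% | 86% | 54% | 54% |
| 70% | 89% | 49% | 59% |

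With SD 10 IU/kg the prophylaxis weight share runs from 19% (no children) to 66% (70% children); with SD 2.5, from 78% to 97%. With the per-kilogram dose unchanged, moving from 10% to 50% children lowers the mean infusion from about 1,930 to 1,500 IU, which is 430 / 1,930 = 22%.

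**5. Whether the planned tables repair this.** The lowest age band in SAP 6.1 is under 30 years, so infants and young adults share it. The under-19 group of SAP 3.3 receives a distribution and adverse event tables (SAP 6.6), but no dose summary. Duration of administration is tabulated separately in SAP 6.5. If the same subjects contribute to both tables, a reader could divide mean total by mean duration for a pooled rate, but could not recover the spread between subjects. Nothing in the listed data allows conversion to IU/kg.

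**The case against.** The strongest reply is that little hangs on these summaries. The study is non-comparative. No test, effective/not-effective classification or decision in the SAP uses dose or consumption, and duration is already shown next to total dosage. That stands, and it keeps the point minor.

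A second reply is that the case report form is not shown. The list in Protocol 7.2.5.1 is not the full data set: SAP 4.2 analyses factor VIII mutation and previous factor VIII therapy, which the protocol list omits. Weight could therefore be on the form, and an unscaled IU summary is an inference from the silence on units. This also stands. What can be said is that weight is not listed and that no unit or scaling is stated.

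A reader might infer more in three directions, and the documents do not support any of them:

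- *That these endpoints mainly measure the age mix.* The documents give no age mix. The statement about newborns says who may be treated, not who was enrolled. In the simulation weight does not dominate in an all-adult sample or in on-demand use with few children, and child/adult status alone reaches at most 54% at SD 5.
- *That the off-label exclusion in SAP 3.1 cannot be applied to dose.* That rule refers to the local product document, which is not available here, and does not mention dose. Under Protocol 7.2.4 the investigator judges whether prescription criteria are met, and does so with the chart at hand.
- *That prophylaxis and on-demand consumption cannot be compared.* No such comparison is planned. The two are summarised separately throughout.

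**Conclusion.** The point holds as a minor reporting defect. As written, the plan yields dose and consumption summaries with no stated unit, confounded by body size and, for total consumption, by observed time. They cannot be set against the 30 ± 5 IU/kg in Protocol 7.2.4. For two individual patients the distortion can be 7-fold at the assumed weights of 10 and 70 kg. For the study means it may be small (a nearly all-adult sample) or considerable (a 22% shift between 10% and 50% children under the simulation's assumptions), and the documents do not allow a choice between these. The dependence on observed time needs no assumption about age; it follows from the data window in Protocol 7.1. The endpoints affected are secondary and descriptive, and the primary objective of detecting factor VIII inhibitor is untouched.

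**What to change.** From data already planned, in SAP 6.5 and 6.7:

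- State the unit of single, mean and total infusion dosage.
- Report total consumption per month or year of each subject's observed time. Define that time, including whether the days after the last dose count.
- Show the dose summaries separately for age under 19 and 19 or over. This is only a partial remedy, since body size still varies widely within the younger group.

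With one added item: put body weight (the chart value nearest the first infusion) into Protocol 7.2.5.1 and SAP 4.1. Report IU/kg per infusion and IU/kg per unit of observed time, with unscaled IU as a secondary row and the number of subjects with missing weight shown.

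The first group costs only programming. The weight item is one chart value for about 95 subjects at 14 sites. Protocol 4 planned data collection to end on 30 September 2017 and the re-examination report for 29 June 2018, while the latest amendment is dated 17 May 2018. Obtaining weight may therefore mean returning to charts after collection has closed, and some values will be missing. If that is not feasible, the first group is still worth doing, with the lack of weight scaling stated as a limitation. All of this concerns reporting only and bears on no dose or clinical rule.

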7.2.5.2. Concomitant Therapy

With regard to all the concomitant therapies, the name, dosage, route of administration, period and treatment purpose should be recorded in the case report form of each study subject.

7.2.5.3. Safety and Efficacy Data

Please refer to Section 7.3 for safety and efficacy data collection.

7.3. Variables

7.3.1. Safety Variables

This study will investigate clinical nature, incidence rates, duration, severity, discontinuation due to adverse events, results and possible causality of adverse events.

7.3.2. Safety Evaluation

7.3.2.1. Definition of adverse events

Adverse events are all the undesirable medical incidents that occur in the study subjects who are administered the drug. Such incidents do not necessarily have causality with the therapy or use of the drug. Examples of adverse events include but are not limited to the following:

- Abnormal test results (see the following for the case where abnormal test results are considered as adverse events.)
- Clinically significant symptoms and signs

- Changes in physical examination findings
- Hypersensitivity reactions
- Progress/deterioration of underlying diseases
- Lack of Efficacy
- Drug abuse
- Drug dependency

Also, drugs may include signs or symptoms due to the following:

- Drug overdose
- Discontinuation of drug administration
- Drug misuse
- Off-label use
- Drug interactions
- Extravasation
- Exposure during pregnancy
- Exposure during breastfeeding
- Medication error
- Occupational exposure

Abnormal test findings

The following is the criteria for deciding whether or not abnormal objective test results should be reported as adverse events:

- If the test result is related to the accompanying symptoms, and/or;
- If the test result requires separate diagnostic examinations or medical/surgical interventions, and/or;
- If the test result causes changes to study dosage or discontinuation of the study, significant additional concomitant drug therapy or other therapy, and/or;
- If the investigator or the sponsor considers the test result as an adverse event.

Abnormal test values that simply repeat and do not correspond to any of the above conditions are not adverse events. All the abnormal test results that are distinguished as errors do not have to be reported as adverse events.

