6. STUDY OBJECTIVE

This study aims to observe the safety and efficacy of the Xyntha Solofuse prefilled syringe in the setting of routine practice. The primary objective is to detect medically significant events

(factor VIII inhibitor). The secondary objective is to observe the overall efficacy and safety of the Xyntha Solofuse prefilled syringe including serious adverse events.

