7.3.2.2. Serious Adverse Events

Serious adverse events or serious adverse drug reactions are undesirable medical incidents as follows:

- If a death is caused;
- If it is life-threatening (risk of an immediate death);
- If hospitalization or extended duration of hospitalization is required;
- If persistent or significant disability or malfunction is induced (substantial disruption in the ability to conduct normal life functions);
- If congenital anomalies/birth defects are induced.

If lack of efficacy is related to any serious adverse event, the lack of efficacy should be reported as an adverse event.

Medical and scientific judgment should be exercised in determining whether or not an adverse event is a significant medical event. A significant medical event may not be immediately life-threatening, or result in death or hospitalization. However, if it is determined that the event may jeopardize the study subject or may require intervention to prevent one of the outcomes as defined as above, it should be reported as a serious adverse event.

Examples of such events include allergic bronchospasm requiring intensive care in the emergency room or at home, blood dyscrasia or convulsions that do not result in hospitalization, or development of drug dependency or drug abuse.

Hospitalization

Hospitalization is defined as all initial admission to the hospital or health facility equivalent to the hospital (including admission for less than 24 hours) or extended duration of the existing hospitalization. Hospitalization also includes the transition to the acute/intensive care unit within the hospital (e.g. from psychiatry to the internal medicine ward, from the internal medicine ward to the cardiovascular disease intensive care unit, or from neurology to the tuberculosis unit). Emergency room visits do not necessarily mean hospitalization, but the event that causes the emergency room visit should be evaluated for its medical significance.

When adverse medical events do not occur, hospitalization itself cannot be seen as an adverse event and should not be reported. For example, the following hospital admission involving no adverse events is not reported:

- Social hospitalization (e.g. the study subject has no place to stay)
- Administrative hospitalization (e.g. for annual periodical medical examination)

- Optional hospitalization that is not related to any sudden medical adverse events (e.g. for plastic surgery chosen by the subject)

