7.3.2.4. Laboratory Test Data

Laboratory tests do not have to be conducted because this study is a non-interventional study. After the investigator conducts laboratory tests for diagnosis and monitoring by methods of general medical practice, the results can be collected. First, indicate whether the test was conducted by marking with either “Not tested” or “Tested”.

- Test Items: Record the items for which abnormal test measurements have been found.
- Normal value range (unit): Record the normal range of the relevant institution with the unit for each item entered.
- Date of Test: Record in the order of year/month/day.
- Pre-dose/post-dose: Record the test measurements.

If “Tested” is marked, check “Yes”, “No” or “Not tested during drug administration” to indicate if there has been a clinically significant abnormality after drug administration

compared to before drug administration. If “Yes” is checked, record details for the following items:

See Section 7.3.2.1 to decide if the clinically significant abnormality should be reported as an adverse event. If it meets the pertinent criteria, it should be recorded in the adverse event section of the case report form.

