2.1. Objectives

This study aims to observe the safety and efficacy of the Xyntha Solofuse prefilled syringe in the setting of routine practice. The primary objective is to detect medically significant events (factor VIII inhibitor). The secondary objective is to observe the overall efficacy and safety of the Xyntha Solofuse prefilled syringe including serious adverse events.

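### A positive inhibitor test with no symptoms, work-up or treatment change is an adverse event only by judgment, so the primary-objective event can be under-counted

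*Protocol*

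**What the plan says.** **Objective.** Protocol 6 states: "The primary objective is to detect medically significant events", and names the factor VIII inhibitor in brackets. SAP 2.1 repeats this.

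**Collection.** Protocol 7.2.5.1 item 6 collects inhibitors within the biochemistry tests, and SAP 4.6(2) lists the item among the laboratory tests. Protocol 7.3.2.4 does not require any test to be done.

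**Laboratory page.** Under 7.3.2.4 the investigator marks whether a test was done, then whether there was a clinically significant abnormality after dosing compared with before. Details follow if the answer is yes. For AE status the section points back: "See Section 7.3.2.1 to decide if the clinically significant abnormality should be reported as an adverse event".

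**Abnormal-test rule.** Protocol 7.3.2.1 gives four alternative conditions, any one of which is enough:
- first, symptoms go with the abnormal value;
- second, more work-up or treatment is needed, in the protocol's words: "If the test result requires separate diagnostic examinations or medical/surgical interventions, and/or";
- third, dosing is altered or stopped because of it, or substantial extra therapy is given;
- fourth, the investigator or the sponsor regards the result as an AE.

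It then adds: "Abnormal test values that simply repeat and do not correspond to any of the above conditions are not adverse events". Lack of efficacy appears separately among the examples of AEs.

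**Seriousness.** Protocol 7.3.2.2 says: "Medical and scientific judgment should be exercised in determining whether or not an adverse event is a significant medical event". Its examples do not include inhibitors.

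**Analysis.** SAP 6.6(1) gives number of subjects, incidence proportion, 95% CI and number of events by system organ class and preferred term, for AEs. SAP 6.6(6) compares laboratory values before and after dosing with a paired test, if possible. Neither document plans a count of new inhibitors.

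**The concern.** The study has one primary event, and no section says that an incident case of it is an AE. Its route into the AE tables is a rule written for laboratory values in general. If a positive post-dose result comes with no symptoms, no further examination and no change of treatment, only the judgment of the investigator or sponsor makes it an AE. As 7.3.2.4 is worded, the investigator must also first mark the abnormality as clinically significant before its details are recorded, so an investigator's no could keep the result from the sponsor as well.

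At stake is the answer to the primary objective. With fewer than a hundred subjects expected, one case separates an inhibitor observed from none observed.

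**Working it through.** The documents contain no sample-size or precision calculation to reproduce (Protocol 7.5 and SAP 2.4 say none applies). The main check is therefore a reading of the text; the arithmetic after it only illustrates the consequence.

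**1. Which inhibitors become AEs under Protocol 7.3.2.1?**

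| Post-dose inhibitor | Condition met | Does AE status rest on discretion alone? |
|---|---|---|
| With symptoms | first | No |
| Prompts further examination or intervention | second | No |
| Leads to dosage change, discontinuation or significant added therapy | third | No |
| Shows as lack of efficacy | listed AE example | No |
| None of these | fourth only | Yes |

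Only the last row is the gap.

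**2. Does another planned output count that last row?**
- SAP 6.6(1) takes AEs only.
- SAP 6.6(6) summarises laboratory values before and after dosing and tests the difference. It does not classify subjects as new cases, and it is conditional.
- Protocol 7.7.1 lists clinically significant laboratory abnormalities as a safety parameter but plans no inhibitor incidence. Protocol 7.7.2.1 confines the laboratory analysis to abnormalities already reported as AEs.

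So no planned table gives a count and CI for inhibitors outside the AE page.

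**3. What would one missed case do?** Inputs: N = 86, the minimum number with safety information in Protocol 5, and the 95% level from SAP 6.6(1). Exact (Clopper-Pearson) limits for x cases are the 0.025 quantile of Beta(x, N − x + 1) and the 0.975 quantile of Beta(x + 1, N − x).
- 0/86: 0%; upper limit 1 − 0.025^(1/86) = 4.20%.
- 1/86: 1.16%; lower limit 1 − 0.975^(1/86) = 0.03%; upper limit 6.31%.
- 2/86: 2.33%; limits 0.28% and 8.15%.

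**4. Chance that at least one case appears in the AE tables.** This is 1 − (1 − p·s)^86, where p is the true inhibitor risk and s the share of cases that reach the AE page. Both are assumptions; the documents give neither.

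| p | s = 1 | s = 0.75 | s = 0.5 | s = 0.25 |
|---|---|---|---|---|
| 1% | 57.9% | 47.7% | 35.0% | 19.4% |
| 2% | 82.4% | 72.7% | 57.9% | 35.0% |
| 3% | 92.7% | 85.9% | 72.7% | 47.7% |

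**5. Denominator.** Steps 3 and 4 treat all 86 subjects as tested, which the protocol does not require. If, as an assumption, half were tested (43), no positives would give an upper limit of 1 − 0.025^(1/43) = 8.2%, against 4.20% with 86.

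**The case against.** The strongest reply is that the rule already captures an inhibitor that matters clinically. Three of the four conditions are stated as facts about the result, two of them need no symptoms, and lack of efficacy is an AE example in its own right. This stands. A reader might infer that the primary event reaches the AE tables only at someone's discretion; the text does not support that beyond the residual case.

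The exclusion sentence is also narrower than it first looks. It covers values that merely recur and meet no condition. Since patients with a history of inhibitors are excluded at entry, a first positive result is not obviously such a value. This stands too, but it does not close the gap: a first positive result meeting none of the first three conditions still has only the opinion-based route.

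A reader might further infer that the AE rule hides the case from every analysis, so that a change to the SAP could not help. That goes too far. The laboratory page is a separate source, SAP 4.6(2) lists the inhibitor item, and SAP 6.6(6) does not require AE status. A table counted from laboratory data could bypass the AE rule. What remains is that no such table is planned and that laboratory details depend on the investigator's first mark.

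On seriousness, the examples in 7.3.2.2 are not exhaustive. Protocol 9 sends both serious and non-serious AEs to the sponsor's safety group within 24 hours when they are clearly attributed to the product, so a non-serious label would not in itself slow the report. The omission of inhibitors from 7.3.2.2 is a mismatch with Section 6, not proof that cases would be misclassified.

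**Conclusion.** The concern holds in a limited form. A post-dose positive inhibitor result with no symptoms, no further work-up and no treatment change is an AE only if the investigator or sponsor considers it one, and its laboratory details depend on the investigator first marking a clinically significant abnormality. Because the AE tables are the only planned output with a count and CI by event term, the primary-objective event can be under-counted by a team that follows the plan as written.

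The size of the under-count cannot be determined, because the documents do not say what share of inhibitors falls in the residual case. The contrast between 1/86 and 0/86 shows how much one case matters if it is missed; it should not be read as an estimate of loss. It also assumes that all 86 subjects were tested. Nor do the documents support treating every inhibitor as serious by rule, or taking 0.6 BU/mL as a ready-made case definition. That figure comes from a baseline exclusion criterion whose wording joins it, as an alternative, to titres inside the laboratory's normal range.

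**What to change.** 1. In Protocol 7.3.2.1 and 7.3.2.4, state that every incident inhibitor, whether a positive post-dose laboratory result or a clinical diagnosis, is recorded on both the laboratory and AE pages regardless of symptoms or treatment change.
2. Clarify the titre wording in Protocol 7.2.2 and 7.7.2 and SAP 2.3.2 before using it as the threshold for an incident case.
3. Reconcile Protocol 7.3.2.2 with Section 6 on how the seriousness of an inhibitor is assigned.
4. Add to SAP 6.6 an inhibitor count and incidence with exact 95% CI, drawn from laboratory and AE data together, with the number tested after dosing as denominator. List clinically diagnosed cases without a post-dose test separately, so that the numerator stays within the denominator.

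The cost is a few sentences in each document, slightly higher AE counts, and a re-check of inhibitor results already in the charts. No patient needs further testing. The re-check is not free: Protocol 4 plans the end of data collection for 30 September 2017 and Protocol 7.5 names 14 sites, so it may mean going back to sites after collection has closed. The SAP table alone, built from laboratory data already held, costs less, but would still miss any result whose details were never entered.
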